9.4.4 Supportive Secondary Efficacy Endpoints and Analyses

No supportive secondary endpoints and analysis are planned.

[figure not shown]
9.5 Additional Efficacy Endpoints and Analyses

The additional endpoints for Period 1 are as follows:

- Proportion of subjects in complete remission at Week 12
- Change from Baseline in SF-36 by visit#
- Change from Baseline in FACIT-Fatigue by visit
- Assessment of TSQM patient global satisfaction subscale by visit
- Change from Baseline in EuroQoL Five Dimensions Five Levels Questionnaire (EQ-5D-5L) by visit
- Assessment of Patients' Global Impression of Change (PGIC) by visit*
- Change from Baseline in Patient Global Assessment (PGA) by visit
- Proportion of subjects with GCA-related Health Resource Utilization by visit
- Proportion of subjects in remission at each visit through Week 52. Defined as:
 - Absence of GCA signs and symptoms
 - o Adherence to the protocol-defined CS taper regimen
- # SF 36 includes PCS, MCS and the 8 sub domains.
- * The assessment of PGIC is defined as achievement of "Very much improved" or "Much improved" on PGIC.

The additional endpoints for Period 2 are as follows:

- Time to first disease flare from onset of Period 2 through Week 104. Disease flare is defined as an event determined by the investigator to represent recurrence of GCA signs or symptoms or an ESR measurement > 30 mm/hr attributable to GCA AND requiring initiation of CS.
- Proportion of subjects maintaining remission from onset of Period 2 through Week 104. Remission is defined as absence of GCA signs and symptoms and CS-free.
- Cumulative CS exposure (Period 2 and inclusive of Periods 1 and 2) through Week 104
- Proportion of subjects in complete remission at Week 104. Complete remission is defined as having achieved all of the following:
 - Absence of GCA signs and symptoms;
 - O Normalization of ESR (to \leq 30 mm/hr); if ESR > 30 mm/hr and elevation is not attributable to GCA, this criterion can still be met;
 - \circ Normalization of hsCRP (to < 1 mg/dL); and
 - CS-free.
- Proportion of subjects who experience at least 1 disease flare from onset of Period 2 through Week 104
- Number of disease flares per subject from onset of Period 2 through Week 104

- Change in SF-36 from onset of Period 2 through Week 104[#]
- Change in FACIT-Fatigue from onset of Period 2 through Week 104
- Assessment of TSQM patient global satisfaction subscale from onset of Period 2 through Week 104
- Change in EQ-5D-5L from onset of Period 2 by visit through Week 104
- Assessment of PGIC from onset of Period 2 through Week 104*
- Proportion of subjects with GCA-related Health Resource Utilization at Week 104
- F SF 36 includes PCS, MCS and the 8 sub domains.
- * The assessment of PGIC is defined as achievement of "Very much improved" or "Much improved" on PGIC.

For the additional endpoints for Period 1, comparison between upadacitinib and placebo treatment groups will be performed on FAS1. Similar analysis methods and intercurrent events handling approaches as primary and secondary endpoints will be used for each type of endpoint as applicable.

Descriptive summaries based on the AO data will be provided for each of the two components of remission at each visit through Week 52, as well as each GCA sign or symptom.

For the additional endpoints for Period 2, comparisons will be performed for the following treatment sequences on FAS2 using similar analysis methods and intercurrent events handling approaches as were used for the primary and secondary endpoints.

Upadacitinib 15 mg QD + 26 weeks CS taper/Upadacitinib 15 mg QD vs.

Upadacitinib 15 mg QD + 26 weeks CS taper/Placebo

Upadacitinib 7.5 mg QD + 26 weeks CS taper/Upadacitinib 7.5 mg QD vs.

Upadacitinib 7.5 mg QD+ 26 weeks CS taper/Placebo

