In Period 2, subjects from the Period 1 upadacitinib group who achieve remission for at least 24 weeks prior to the Week 52 visit (at the end of Period 1) will be re-randomized to either continue on upadacitinib or switch to PBO (Section 4.1); re-randomization will be stratified by baseline disease status (new onset or relapsing disease). Subjects from the Period 1 Placebo group who achieve remission for at least 24 weeks prior to the Week 52 visit (at the end of Period 1) will continue to receive PBO. In Period 2, subjects previously on upadacitinib will be re-randomized in a 2:1 ratio (upadacitinib [same dose as Period 1] or PBO). Subjects who were assigned to PBO in Period 1 will continue to receive PBO. At Week 52, subjects who have absence of GCA signs and symptoms AND are CS-free, but do not meet the above remission criteria will continue in Period 2 on their originally randomized treatment assignment. All other subjects will be discontinued from study drug at the end of Period 1.

All AbbVie personnel with direct oversight of the conduct and management of the trial (with the exception of AbbVie Drug Supply Management Team) will remain blinded to each subject's treatment until the last subject completes the Week 52 visit. After the last subject completes the Week 52 visit the Sponsor will be unblinded to Period 1 and Period 2 study drug assignments to facilitate regulatory filings. The investigator, study site personnel, and the subject will remain blinded to each subject's treatment throughout the study. To maintain the blind, upadacitinib tablets and matching PBO tablets as well as CS capsules and matching PBO capsules provided for the study will be identical in appearance. The IRT will provide access to unblinded subject treatment information in the case of a medical emergency.

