Additional efficacy variables are listed in Section 3.3 and will be summarized for Period 1 and 2. For all the additional efficacy variables in Period 1, the summary statistics and the statistical method will be the same as the corresponding variables described in the primary and key secondary analyses. For all the additional efficacy variables in Period 2, descriptive statistics will be provided for each treatment group sequence. For binary endpoints, frequencies and percentage with 95% CI using normal approximation will be reported for each treatment group and 95% CI will be reported for treatment difference. For continuous endpoints, the mean, standard deviation, 95% CI, median, and range will be reported for each treatment group and 95% CI will be reported for treatment difference. For time-to-event endpoints, median time-to-event will be reported for each treatment group. For count endpoints, the exposure duration adjusted event rates will be reported for each treatment group.

Sample Size Estimation

The planned total sample size of 420 subjects with a 2:1:1 ratio (upadacitinib 15 mg QD: upadacitinib 7.5 mg QD: PBO QD) was determined to have at least 90% power to detect a 20% difference in sustained remission rate at Week 52 between the upadacitinib 15 mg arm and the PBO arm (assuming a response rate of 40% in the PBO arm), using Fisher's exact test, with an overall two-sided alpha = 0.05.

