- The estimand corresponding to the multiplicity-controlled secondary endpoint of time to first disease flare is defined as the difference in the time to first disease flare in either upadacitinib 15 mg QD or 7.5 mg QD in combination with a 26-week CS taper regimen group and placebo in combination with a 52-week CS taper regimen group in subjects with GCA, regardless of premature discontinuation from study drug, or receiving more than 100 mg prednisone (or equivalent) systemic CS for a non-GCA indication.
- The estimand corresponding to the multiplicity-controlled secondary endpoint of number of disease flare per subject is defined as the difference in the

exposure-adjusted number of disease flare per subject between either upadacitinib 15 mg QD or 7.5 mg QD in combination with a 26-week CS taper regimen group and placebo in combination with a 52-week CS taper regimen group in subjects with GCA, regardless of premature discontinuation from study drug, or receiving more than 100 mg prednisone (or equivalent) systemic CS for a non-GCA indication.

The objective of Period 2 is to evaluate the safety and efficacy of continuing versus withdrawing upadacitinib in maintaining remission in subjects who achieved remission in Period 1.

[figure not shown]

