Subjects assigned to either dose of upadacitinib who achieve sustained remission for at least 24 consecutive weeks prior to the Week 52 Visit (at the end of Period 1) will be rerandomized in a 2:1 ratio to either continue on upadacitinib or switch to placebo in Period 2. Re-randomization will be stratified by Baseline disease status (new onset disease, relapsing disease). Subjects who achieved sustained remission for at least 24 consecutive weeks prior to the Week 52 visit (at the end of Period 1) who were assigned to placebo in Period 1 will continue to receive placebo in Period 2.

At Week 52, subjects who have absence of GCA signs and symptoms AND are CS-free, but do not achieve sustained remission for at least 24 consecutive weeks prior to the Week 52 Visit will continue in Period 2 on their originally randomized treatment assignment. All other subjects will be discontinued from study drug and the study at the end of Period 1.

In Period 2, subjects who experience a flare will start open-label CS escape therapy with prednisone or prednisolone at investigator's discretion. Subjects meeting flare criteria will return within approximately 4 weeks after the visit in which flare was determined for reassessment (either at a regularly scheduled or unscheduled visit). If the subject does not have absence of GCA signs and symptoms within approximately 4 weeks after the visit in which flare was determined, they will be discontinued from study drug. Subjects who discontinue study drug should receive treatment at the investigator's judgment, in accordance with local standard-of-care (which could include tocilizumab) and continue to follow the regular visit schedule for Period 2 and adhere to the study procedures.

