9.0 Efficacy Analyses

9.1 General Considerations

All efficacy analyses will be conducted on the FAS in each period. All Period 1 efficacy analyses will be conducted using FAS1. All Period 2 efficacy analyses will be conducted using FAS2. In addition, per-protocol analysis for the primary endpoint will be performed in the Per-Protocol Analysis Set.

The Primary Analysis will be performed after all subjects have completed Period 1 and the database has been locked. This will be the final analysis for all primary and multiplicity-controlled secondary endpoints as well as all additional efficacy endpoints in Period 1.

The primary and multiplicity-controlled secondary endpoints as specified in Section 3.0 will be tested with graphical multiplicity adjustment 1,2 to ensure a strong control of family-wise type I error rate at 2-sided $\alpha = 0.05$.

[figure not shown]
The final analysis will be performed after all subjects have either withdrawn from the study or completed Period 2 and safety follow-up.

For analyses with stratification factors used for randomization, any subject who is randomized within an incorrect stratum will be analyzed according to the actual stratum to which the subject belongs, unless otherwise indicated. The stratification factor of prior use of an IL-6 inhibitor (yes, no) will be removed from the models for all analyses due to the small number (17 [approximately 4.0%] out of 428 total) of prior IL-6 inhibitor users enrolled.

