9.3.2 Main Analysis of Primary Efficacy Endpoint

The statistical null hypothesis corresponding to the primary endpoint is that there is no difference between either upadacitinib 15mg QD or 7.5mg QD in combination with a 26-week CS taper regimen group and the placebo in combination with a 52-week CS taper regimen group in terms of the proportion of subjects achieving sustained remission at Week 52 in Period 1.

Analysis of the primary endpoint will be conducted on the FAS1 based on treatment as randomized. Comparison will be made between each upadacitinib group and placebo group using the Cochran-Mantel-Haenszel (CMH) test for common risk difference estimated by a weighted average of risk difference across strata using the Mantel-Haenszel weights. The strata include stratification factors (Baseline CS dose [prednisone or prednisolone > 30 mg, prednisone or prednisolone ≤ 30 mg], and Baseline disease status [new onset disease, relapsing disease]). NRI-MI will be the primary approach in handling missing values. Point estimate, p-value, and 95% CIs for the difference in proportions between each upadacitinib group and placebo group will be provided.

The attributes of the estimand corresponding to the primary efficacy endpoint are summarized in Table 1.

Table 1. Summary of the Estimand Attributes Corresponding to the Primary Efficacy Endpoint

	Attributes of the Estimand					
Estimand Label	Treatment	Endpoint	Population	Handling of Intercurrent Events	Statistical Summary	
Primary	Upadacitinib vs. Placebo	Achievement of sustained remission at Week 52	Subjects with GCA	 ICE1: composite Subjects will be considered as non-responders after ICE1. ICE3: hypothetical Data after ICE3 will be imputed by MI. 	Difference in proportion of subjects achieving sustained remission at Week 52	

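### Period 2 binary endpoints get large-sample intervals, and by natural reading the Period 1 four-cell strata, in re-randomised groups small enough for coverage to fall below 95%

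*SAP*

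**What the plan says.** SAP 2.1 sets the aim: "The objective of Period 2 is to evaluate the safety and efficacy of continuing versus withdrawing upadacitinib" among subjects who reached remission. For the Period 2 endpoints, SAP 9.5 states that "comparisons will be performed for the following treatment sequences on FAS2 using similar analysis methods" as the primary and secondary endpoints. It lists two comparisons, continue versus withdraw within 15 mg and within 7.5 mg, and names no strata, interval method or sparse-data rule for them.

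The primary method in SAP 9.3.2 is a common "risk difference estimated by a weighted average of risk difference across strata using the Mantel-Haenszel weights". Its strata are spelled out: "The strata include stratification factors (Baseline CS dose [prednisone or prednisolone > 30 mg, prednisone or prednisolone ≤ 30 mg], and Baseline disease status". The third Period 1 factor, prior IL-6 inhibitor use, "will be removed from the models for all analyses due to the small number (17 [approximately 4.0%] out of 428 total" (SAP 9.1). That leaves 2 × 2 = 4 cells.

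Period 2 was randomised differently. SAP 2.3 says "Re-randomization will be stratified by Baseline disease status (new onset disease, relapsing disease", and Protocol 5.9 agrees: "re-randomization will be stratified by baseline disease status (new onset or relapsing disease". That gives two cells.

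Protocol 7.3 calls the Period 2 efficacy results descriptive. For binary endpoints it says "frequencies and percentage with 95% CI using normal approximation will be reported for each treatment group", and it asks for a 95% interval on the treatment difference without naming the method. The rule that drops stratification when a stratum is empty stands in SAP 9.6 and is worded for subgroup analyses of the primary endpoint.

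**The concern.** Methods chosen for 210 versus 105 subjects are carried into groups that may be under a sixth of that size. Wald-type intervals are too short in small samples, especially when the true rate is near 0 or 1. Splitting the same subjects over four cells makes this worse, and a cell with nobody in one group gets zero weight, so its subjects in the other group leave the estimate. Only one of the two carried-over factors was used in the re-randomisation.

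Period 2 has no powered or multiplicity-controlled test, so the interval is the result that readers will use to judge withdrawal. If it is too short, the evidence looks firmer than it is, most of all for 7.5 mg.

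**Working it through.** **Plan's own figure.** Exact enumeration of Fisher's test for 210 versus 105 at 60% versus 40%, two-sided 0.05, gives 91.0% power. This agrees with the stated figure of at least 90% (SAP 2.4). The documents give no size, power or coverage figure for Period 2.

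**Group sizes.** Arm sizes are from Protocol 4.1, and the 2:1 split is from SAP 2.3. The share qualifying for FAS2 is not given. I assume 40–60%, the planned placebo and 15 mg rates for the primary endpoint.
- 7.5 mg: 105 × 0.40 = 42, split 28:14; 105 × 0.60 = 63, split 42:21.
- 15 mg: 210 × 0.40 = 84, split 56:28; 210 × 0.60 = 126, split 84:42.

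**Mantel-Haenszel difference.** In cell k, with x₁ of n₁ continuing and x₀ of n₀ withdrawn, and n = n₁ + n₀:
- Weight w = n₁n₀/n, so w = 0 if either group is empty. Estimate d = Σw(p̂₁ − p̂₀)/Σw.
- Stratum-wise variance: Σw²[p̂₁(1 − p̂₁)/n₁ + p̂₀(1 − p̂₀)/n₀]/(Σw)².
- Sato variance: (dΣP + ΣQ)/(Σw)², where P = [n₁²x₀ − n₀²x₁ + n₁n₀(n₀ − n₁)/2]/n² and Q = [x₁(n₀ − x₀) + x₀(n₁ − x₁)]/(2n).

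The documents do not say which variance applies, so both are shown. The simulation used 2:1 blocks within disease status, with starting dose left to chance. Assumed ranges: outcome rates 60–90% continuing versus 40–70% withdrawn; new-onset share 30–50% (the plan's minimum is 30%); one dose level 30–50%. There were 6,000 runs per scenario at 42 and 63, and 3,000 at 126. At 6,000 runs and 90% coverage the simulation error is √(0.9 × 0.1/6000) ≈ 0.4 points.

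| FAS2 in the dose arm | Stratum-wise, four cells | Sato, four cells | Trials with an unmatched cell | Mean subjects lost |
|---|---|---|---|---|
| 42 (28:14) | 87.4–90.1% | 91.0–93.0% | 4–32% | 0.3–0.9 |
| 63 (42:21) | 90.7–91.9% | 92.8–93.9% | 0.3–14% | 0.0–0.5 |
| 126 (84:42) | 92.2–94.2% | 93.4–95.4% | at most 1.5% | at most 0.1 |

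For 15 mg at 40% qualifying (56:28), coverage is about 92–95% over both variances.

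**Disease status only (two cells), stratum-wise variance.** Coverage is 91.0–92.3% at 42 and 92.3–93.1% at 63, with essentially no unmatched subjects.

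**No strata, exact enumeration.** The Wald difference covers 91.7–93.2% at 28 versus 14 and 93.4–94.1% at 42 versus 21. Newcombe covers 93.7–95.9% and 93.9–95.5%.

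**Single groups, p̂ ± 1.96√[p̂(1 − p̂)/n].**
- n = 14, p = 0.9: the interval contains 0.9 only for 10 to 13 responders. At 14 of 14 it collapses to a point, with probability 0.9¹⁴ = 0.229. Nine or fewer has probability 0.009. Coverage is 1 − 0.229 − 0.009 = 76.2%, and by symmetry the same at p = 0.1.
- n = 14, p from 0.2 to 0.8: 92.1–94.4%.
- n = 21, p = 0.3, 0.7 or 0.9: 89%.
- Wilson covers about 95% at n = 14, p = 0.9 and at the three n = 21 settings. It is not exact everywhere: at n = 21, p = 0.5 both intervals cover only for 7 to 14 responders, so both give 1 − 2 × 0.0392 = 92.2%.

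**The case against.** The strongest reply is that the plan never says four cells. SAP 9.5 says only that methods are similar, and SAP 9.1 speaks of the factors used for randomisation, which in Period 2 means disease status alone. This stands as a possible reading. It removes the lost subjects and the 87% figure, but coverage at 28 versus 14 is still 91–92%, so the interval method matters under either reading. The strata that SAP 9.3.2 and 9.4.2 write out are the four-cell ones, and nothing replaces them for Period 2.

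Four stronger conclusions that a reader might infer are not supported.
- **That Period 2 intervals in general cover 87–92%.** That range needs the 7.5 mg arm, four cells and a stratum-wise variance that the plan does not specify. The 15 mg comparison is near nominal.
- **That all Period 2 error bars are affected.** The figures apply to the Mantel-Haenszel-type binary endpoints. Time to flare uses log-rank and Cox methods, the flare proportion a Kaplan-Meier-based estimate, and most continuous endpoints a repeated-measures model.
- **That 76% is typical.** It needs a true rate of 90% (or 10%) in a group of 14, which here is the withdrawal group. Protocol 2.1 reports that over half of good responders to another drug relapsed after stopping it, which points away from 90% remission after withdrawal.
- **That having no pooled-dose comparison is an error.** The objective does not call for one, and Protocol 4.2 includes 7.5 mg to characterise the minimal efficacious dose, which justifies by-dose results.

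**Conclusion.** The point holds in a limited form. For Period 2 binary endpoints the plan specifies normal-approximation intervals per group. By its natural reading it also applies four-cell Mantel-Haenszel intervals to groups re-randomised on one factor, with no empty-cell rule. In the 7.5 mg comparison the shortfall from 95% is about 3 to 8 points with a stratum-wise variance and 1 to 4 with Sato. It is 0 to 3 points for 15 mg. Single-group intervals can miss by more at high or low rates. Loss of subjects through unmatched cells is possible, not certain, and averages about one or fewer.

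The sizes rest on the assumed 40–60% qualifying share, outcome rates and cell shares; the direction does not depend on their exact values. The results affected are descriptive and outside the multiplicity control, so the primary conclusion of the trial is untouched.

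**What to change.** In SAP 9.5 and Protocol 7.3, state for Period 2 binary endpoints:
- Wilson intervals for single-group proportions.
- Newcombe or Miettinen-Nurminen intervals for differences.
- Disease status, the re-randomisation factor, as the only stratum.
- An unstratified analysis if a stratum is empty in either group.

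The same edit should reconcile the comparisons in SAP 9.5 with the descriptive summary in Protocol 7.3. Changing the strata without the interval method is not enough, as the two-cell results show. The Newcombe figures above are for unstratified groups; coverage of the version stratified by disease status was not computed and should be checked by simulation before the text is final.

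The cost is a few sentences and slightly wider intervals on additional endpoints, with no new data and no design change. A continue-versus-withdraw estimate pooled over doses and stratified by dose could be added, but it is optional and not part of this correction.

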9.6 Efficacy Subgroup Analyses

Subgroup analyses of the primary endpoint will include:

- Sex (Male, Female)
- Age Group 1 (< 65 years, \ge 65 years)
- Age Group 2 (< 65 years, \ge 65 and < 75 years, \ge 75 years)
- Race Group (White, Non-White)
- Baseline BMI Group ($< 25 \text{ kg/m}^2$, $\ge 25 \text{ kg/m}^2$ and $< 30 \text{ kg/m}^2$, $\ge 30 \text{ kg/m}^2$)
- Geographic Region Group (North America, Western Europe, Eastern Europe, Asia, Oceania)
- Nicotine User (Current, Former, Never)
- Prior Use of IL-6 Inhibitor (Yes, No)
- New Onset of GCA (Yes, No)
- Baseline CS Dose ($> 30 \text{ mg}, \le 30 \text{ mg}$)
- Ischemia-Related Vision Loss within 8 Weeks Prior to Baseline (Yes, No)
- History of Unequivocal Symptoms of PMR Symptom without Cranial Symptoms of GCA (Yes, No)

For any subgroup, if there are zero subjects within a stratum in any treatment group, the CMH model will not be adjusted by the stratification factors.

[figure not shown]
Additional subgroup analyses may be conducted as appropriate.

10.0 Safety Analyses

10.1 General Considerations

Unless otherwise specified, safety data will be summarized on SS1 for Period 1, SS2 for Period 2 and SS LT across Period 1 and Period 2. Safety analysis will include adverse events, laboratory, and vital signs measurements. Safety summaries will be presented by treatment group in each safety analysis set, including a total group for all subjects on active study treatment.

For the safety analysis, subjects are assigned to a treatment group based on the treatment actually received, regardless of the treatment randomized.

Missing safety data will not be imputed.

